#### 1.0 Protocol Summary

Title	A prospective, randomized evaluation of the ControlRad system to reduce radiation exposure during cardiac catheterization and electrophysiology procedures		
Design	Prospective, randomized, single center evaluation		
Procedure	40 cardiac interventional procedures and 120 pacemaker and/or ICD procedures		
Objective	To determine whether the ControlRad system reduces radiation exposure to operators, staff and patients during diagnostic and interventional cardiac catheterization procedures and electrophysiology implant procedures		
Enrollment	Prospective		
Site(s)	Beaumont Hospital Royal Oak		
Time Course	2020- 2021		
Primary Outcome	Effective radiation dose to primary operator		
Principal Investigator	r [name]		
Co-Investigators	[name], [name], [name] Study Coordination Beaumont Hospital Royal Oak		

# 2.0 Background

# 2.1 Current Approaches for Radiation Protection

Long-term radiation exposure in the cardiac catheterization laboratory is associated with an increased risk of premature cataract formation, chromosomal damage, subclinical atherosclerosis and cancer (1-4). Conventional approaches to limit radiation exposure include a) wearing lead apparel, b) positioning table and ceiling-mounted radiation shields between the operator and patient, and c) technical considerations such as reducing the fluoroscopic frame rate, minimizing fluoroscopic time and acquisition runs, maintaining the optimal table height and image intensifier position, and use of filters and collimators in the imaging chain (5,6).

Despite these approaches, physicians working in the cardiac catheterization laboratory continue to receive high doses of radiation, primarily attributable to scatter radiation from the patient. This situation has in part been compounded by the increasing complexity of therapeutic procedures, such as interventions for chronic total occlusion. Prior studies have demonstrated that the primary operator is subject to the highest radiation dose due to proximity to the primary radiation beam, but other operators and staff also receive significant occupational exposure. Because of these concerns, there

has been a clear need to develop new methods to reduce radiation exposure to physicians and staff in the cardiac catheterization laboratory.

# 2.3 Pre-Clinical Data

The ControlRad system was evaluated in a swine model of iliac and renal artery stenting (7). Radiation dose measurements were obtained with and without the ControlRad system.

As shown below, there was a significant reduction in baseline radiation dose to both the operator and animal with the ControlRad system. The overall effect was a radiation reduction of approximately 75% relative to baseline dose.

	Without	With	p-value
Total kerma air product (µGym2)	635	124	<0.001
Total air kerma (mGy)	3394	1061	<0.001
Dosimeter (mR/h)	20.5	6.3	<0.001

#### 3.0 Study Design

3.1 Objectives

To determine whether the ControlRad system reduces radiation dose to operators, staff and patients during diagnostic and interventional cardiac catheterization and electrophysiology (EP) implant procedures

- 3.2 Design Prospective, randomized single center evaluation
- 3.3 Study Population
  - Patients scheduled for cardiac catheterization in cath lab 5 at Beaumont Royal Oak.
  - Enrolment will continue until 40 patients undergoing intervention have been recruited. (The total patient population is estimated to be 200 given the current diagnostic cardiac catheterization to interventional cardiac catheterization case ration is 2:1 which may fluctuate more participants are enrolled.)
  - EP patients scheduled for a Pacemaker or ICD in cath lab 5 at Beaumont Royal Oak Hospital. Enrollment will continue until 30 patients undergo a complex procedure in the EP lab. (The current patient population is estimated to be 120 given the simple to complex case ratio which may fluctuate as more participants are enrolled.)
  - Physicians and staff
    - For each procedure, 3 staff members will be study subjects: a) the primary operator, b) the secondary operator, c) the nurse/tech who circulates in the room
    - Different operators and staff may participate in each case depending on cath lab scheduling. The cath lab has 20 cardiology fellows, 35 interventional cardiologists and 56 staff, all of whom may participate in the study

# 3.4 Inclusion Criteria

Subjects will be eligible to participate if the following criteria are met:

- Patient
  - Scheduled to undergo left heart catheterization with angiography, and/or percutaneous coronary intervention
  - o Scheduled to undergo pacemaker or ICD implant
  - EP device upgrade
  - o Able to provide written informed consent prior to the procedure
  - Age ≥18 years
- Physicians and Staff
  - Able to provide consent for the study
- 3.5 Exclusion Criteria

Subjects will not be eligible to participate if any of the following criteria are met:

- Patient
  - o Cardiogenic shock

IRB NUMBER: 2019-174 IRB APPROVAL DATE: 07/14/2021

- Reason for cath procedure is pericardiocentesis
- o Subcutaneous ICDs
- o Lead revisions
- Inability to provide informed consent
- o Pregnant
- Physicians and Staff
  - o Those who are not willing to participate in the study
- 3.6 Study Endpoints

**Primary Endpoint** 

Mean effective radiation dose (µSv) to the primary operator

Secondary Endpoints

- Mean effective radiation dose (µSv) to the secondary operator
- Mean effective radiation dose (µSv) to the circulating nurse
- Mean radiation dose to the patient (dose-area product, DAP)
- Mean radiation dose ( $\mu$ Sv) at a standard location on the wall of the cath lab
- 3.7 Definitions
  - Primary operator is the physician who usually stands nearest to the C-arm. This is generally the attending physician in the EP cases and a fellow in cath lab
  - Secondary operator is the physician or scrub assistant (nurse or technician) who typically stands to the right of the primary operator and in most cases is the attending physician in the cath lab.
  - Nurse or Anesthesia team typically circulates in the room and is responsible for monitoring the patient, administering medications and obtaining equipment for the procedure

# 4.0 Conduct of Study

4.1 Screening

Patient

- All patients who are scheduled for cardiac catheterization in Cath Lab 5 will be considered for inclusion in the study.

Physicians and Staff

- Physicians and staff who work in Cath Lab 5 will be considered for participation in the study.
- 4.2 Informed Consent

Patient

Written informed consent will be obtained from the patient by the research coordinator or investigator.

Physician and Staff

Physicians and staff who work in Cath Lab 5 will be provided an information sheet regarding the study. The principal investigator will assist in informing the physicians and staff about the study, but will not participate in the consent process. Consent will be obtained by the research coordinator and will continue for the duration of the study. A physician or staff member may withdraw consent at any time during the study. Scheduling of procedures and staff will be determined by the cath lab manager/scheduler according to usual schedules and lab availability. If a patient, physician or staff member declines participation, the procedure will be scheduled in another cath lab.

#### 4.3 Randomization

Procedures will be randomized 1:1 using sealed envelopes provided by the study statistician to either cardiac catheterization without ControlRad or cardiac catheterization with the ControlRad system. The same 1:1 randomization process will be applied to the EP patient population. Patients will be blinded to the randomization.

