# 5.3 Power Analysis

In 2017, the median total air kerma dose (TAK) for a diagnostic and PCI in Cath Lab 5 was 460 mGy and 1577 mGy respectively. Approximately 50% of the TAK for a diagnostic or PCI procedure is from fluoroscopy and 50% from cineangiography. In pre-clinical studies the ControlRad system reduced radiation dose by 75% during fluoroscopy. Using PASS 14 Power Analysis and Sample Size Software (2015). NCSS, LLC. Kaysville, Utah, USA, ncss.com/software/pass, we found that 9 diagnostic patients and 6 PCI patients per arm would give us 80% power to detect that absolute difference of 20% with a 0.05 significance level. Allowing for some variation in the actual frequencies in this higher risk group of patients or any drop outs, we intend to enroll 30 patients per arm.

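### Neither the randomisation (4.3) nor the analysis (5.5) accounts for procedure type, the largest dose driver the plan quantifies; this costs precision, and pre-specified adjustment recovers most of it.

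*Combined protocol and SAP*

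**What the plan says.** Section 4.3 describes allocation in two sentences: "Procedures will be randomized 1:1 using sealed envelopes provided by the study statistician", to catheterization with or without the device, and then "The same 1:1 randomization process will be applied to the EP patient population". It names no strata, blocks or method of generating the list.

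Section 3.4 admits catheterization patients under one criterion, "Scheduled to undergo left heart catheterization with angiography, and/or percutaneous coronary intervention", which does not separate the two types. The EP population mixes simple and complex implants (3.3).

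Section 5.3 treats diagnostic and PCI cases as distinct. It reports that "the median total air kerma dose (TAK) for a diagnostic and PCI in Cath Lab 5 was 460 mGy and 1577 mGy respectively" and sizes the types separately: "9 diagnostic patients and 6 PCI patients per arm would give us 80% power". Section 3.3 recruits until fixed numbers of interventions and of complex EP cases are reached, and Table 1 lists Diagnostic and PCI by arm.

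That distinction does not reach the endpoint or the analysis. Section 3.6 defines the primary endpoint as one mean effective dose to the primary operator. Section 5.5 specifies intent-to-treat and descriptive statistics, with no test, covariate, transformation or by-type comparison.

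**The concern.** When one kind of case carries about three times the dose of another, an overall mean by arm depends on how many of each kind the arm happened to receive. Unless allocation or analysis controls this, between-type variation stays in the error term. Two things are at stake. The first is power: a real reduction is harder to detect than it needs to be. The second is interpretation: in any one trial, part of the observed difference may be case mix, and a plan that is silent on adjustment leaves the remedy to be chosen after the data are seen.

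**Working it through.** **Inputs from the documents.** Median air kerma 460 mGy (diagnostic) and 1577 mGy (PCI); target "absolute difference of 20% with a 0.05 significance level"; "Approximately 50% of the TAK for a diagnostic or PCI procedure is from fluoroscopy"; "the ControlRad system reduced radiation dose by 75% during fluoroscopy" (all 5.3). Catheterization sample size: 60 (30 per arm, 5.3; also Table 1), about 200 (3.3), or 120 if the 40 interventions and 2:1 ratio of 3.3 are taken together (40 × 3).

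**Assumptions.** Medians are used as typical doses. The air kerma ratio is carried over to operator dose, because no operator dose by type is given. No within-type spread is given, so a range is shown.

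**The plan's own figure.** The 9 and 6 per arm cannot be reproduced, because no SD is stated. Solving a two-sided t-test at 80% power for a 20% effect implies a CV of about 14% (SD 65 mGy) for diagnostic and 11% (SD 176 mGy) for PCI. For a 37.5% effect the CVs are about 27% and 21%. The 37.5% comes from 0.75 × 0.50.

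**Step 1: dose ratio.** 1577 / 460 = 3.43; the difference is 1117 mGy.

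**Step 2: what imbalance does.** With PCI share p, mean dose is 460(1 − p) + 1577p. At p = 1/3 this is 832.3 mGy. A gap of g in PCI share between arms shifts the difference by 1117g, so a shift of 20% of the mean needs g = 0.20 × 832.3 / 1117 = 0.149. At N=200 with 40 PCI the mean is 683.4 and g = 0.122.

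Probability of such a shift in either direction, with no true effect (hypergeometric for equal arms; simulated coin-flip allocation in brackets):

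| N (PCI) | Smallest split reaching 20% | P(shift ≥ 20%) | P(shift ≥ 37.5%) |
|---|---|---|---|
| 60 (20) | 13:7 | 17% (24%) | 1.3% (2.2%) |
| 120 (40) | 25:15 | 8% (8%) | 0.1% (0.1%) |
| 200 (40) | 27:13 | 2% (3%) | under 0.01% |

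Illustration at N=120, 60 per arm, PCI split 24:16. The means are (24 × 1577 + 36 × 460)/60 = 906.8 and (16 × 1577 + 44 × 460)/60 = 757.9. The gap of 148.9 mGy is 17.9% of 832.3, just short of the target. A split this uneven or worse has probability 0.17 with equal arms. If the device truly cuts dose by 20% and its arm has the 24 PCIs, the comparison is 0.8 × 906.8 = 725 against 758, an apparent cut of 4%. Reversed, it is 0.8 × 757.9 = 606 against 907, an apparent cut of 33%.

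**Step 3: precision on log dose, N=120.** The between-type variance is (ln 3.43)² × (1/3)(2/3) = 1.518 × 0.222 = 0.337. The SE of the arm difference is √(4V/120), where V = s² + 0.337 unadjusted and V = s² adjusted.

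| Within-type log-SD s | Unadjusted SE | Adjusted SE |
|---|---|---|
| 0.5 | 0.140 | 0.091 |
| 0.7 | 0.166 | 0.128 |
| 0.9 | 0.196 | 0.164 |

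Simulation gives 0.140, 0.169, 0.195 unadjusted; 0.092, 0.129, 0.166 adjusted after simple randomisation; and 0.092, 0.128, 0.166 with stratified allocation.

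**Step 4: if half the PCIs are ad hoc (an assumption).** Then 20 of the 40 sit among 100 cases scheduled as diagnostic. The between-type variance left after adjusting for scheduled type is 1.518 × (0.2 × 0.8) × 100/120 = 0.202. The SEs become √(4(s² + 0.202)/120) = 0.123, 0.152 and 0.184. The variance reduction falls from 57%, 41% and 29% to 23%, 16% and 12%.

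**Step 5: error rates.** Lognormal simulation, 6,000 runs per setting, raw scale, true 20% effect, simple randomisation, with type known:

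| N | CV 0.3: unadjusted → adjusted power | CV 0.6: unadjusted → adjusted power |
|---|---|---|
| 60 | 19% → 66% | 14% → 23% |
| 120 | 36% → 92% | 25% → 42% |
| 200 | 55% → 99% | 37% → 61% |

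With no effect, the unadjusted test rejected about 5% of the time at every size. Stratified allocation with an unadjusted test was far too conservative: at N=60 and CV 0.3, type I error was about 0% and power for 20% about 3%.

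**The case against.** **The defect lies in 5.5 more than in 4.3.** This stands. The primary endpoint is measured per case, so adjustment is available, and Step 3 shows that stratification adds almost nothing once the model adjusts. It is why the main fix is in the analysis.

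**The plan may intend separate analyses by type.** Section 5.3 sizes the types separately, and analysing them that way would remove the problem. But 3.6 and 5.5 do not say so.

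**PCI status may be unknown when the envelope is opened.** This stands in part. The and/or inclusion criterion does not show that the type is fixed beforehand, and the documents do not say how many PCIs are scheduled. Step 4 shows the smaller gain.

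**The cumulative Landauer badges need balanced arms, because no model can correct them.** They hold no per-case values, so this is true as far as it goes. But they are not a listed endpoint, and one cumulative total per arm at each location (with a backup badge) supports no valid test with or without strata. They are a minor reason to stratify.

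**A stronger reading to resist.** A reader might infer that unstratified allocation biases the trial or readily produces a false positive of the target size. The documents do not support that: randomisation keeps the comparison unbiased on average, and type I error stays near 5%. A misleading result here means one unlucky realisation. Its probability depends on an unreconciled N, and against 37.5% it is rare.

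**Conclusion.** The concern holds as a loss of precision and a risk of a misleading single estimate. Section 5.3 documents a 3.4-fold dose difference by procedure type, and neither allocation nor the stated analysis uses it. Against the plan's 20% target, chance case mix alone matters at about 17-24% probability for N=60, 8% for N=120 and 2-3% for N=200. At N=120, ignoring type raises the SE by roughly a fifth to a half (0.196/0.164 = 1.20; 0.140/0.091 = 1.54) if type is known beforehand.

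These sizes rest on patient air kerma standing in for operator dose, on medians used as typical values, and on an assumed within-type spread. The EP population has the same gap between simple and complex implants, but the documents give no EP doses, so its size cannot be stated. The change is worth making because it is cheap, not because the design is invalid.

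**What to change.** **Main change, section 5.5.** Pre-specify that the primary per-case dose comparison, for example on log dose, is adjusted for procedure type: diagnostic versus PCI in the catheterization population, simple versus complex in the EP population. Use the type scheduled before randomisation in the primary model, and record it on the case report form before the envelope is opened. Use the procedure actually performed in a sensitivity analysis only, since it may be settled after allocation.

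**Addition, section 4.3, for envelopes not yet issued.** Have the statistician prepare separate 1:1 permuted-block series, with varying block size, for scheduled diagnostic, scheduled PCI, simple EP and complex EP. Always pair this with the stratum factor in the model, because stratifying without adjusting gives an over-conservative test. The gain is better balance in unadjusted means and in the descriptive Landauer totals.

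**Cost.** Protocol wording, one recorded field and, if strata are added, four envelope series. Ad hoc PCIs stay in their scheduled stratum, so some imbalance remains. The version reviewed carries a July 2021 IRB approval date and a 2020-2021 time course. If enrolment is under way, used envelopes cannot be re-stratified, but adjustment can still be specified before the dose data are compared by arm.

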#### 4.4 Measurement of Radiation Dose

Two methods will be used to measure radiation dose during the catheterization procedure:

# A. Real-time Dosimeter Badge (RaySafe)

Real-time radiation exposure data will be collected using the commercially available RaySafe dosimetry system (RaySafe i3, Billdal, Sweden). This dosimeter provides the ability to measure radiation dose *per case*.

# B. Landauer Luxel Aluminium Oxide Dosimeter Badges

The Landauer dosimeter badge will provide a *cumulative* radiation dose for each anatomic location. One set of badges will be used for cases performed with ControlRad, and one set for catheterization cases without ControlRad.

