# C. Dosimeter Badge Positions

Prior to each catheterization procedure the radiation badges will be placed at each location by the research coordinator, radiation safety officer, or trained cath lab staff member. The dosimeter badges will be removed at the end of each case. The location of the badges is shown below:

	RaySafe	Landauer
	(Dose Per Case)	(Cumulative Dose)
Primary Operator	Thyroid	Thyroid (2)
	Knee	Inner (2)
Secondary Operator	Thyroid	Thyroid (2)
	Knee	Inner (2)
Nurse	Thyroid	Thyroid (2)
	Knee	Inner (2)

Cath Lab	Wall	Wall (2)

The outer dosimeter badges will be placed on the left anterior side of the thyroid collar and the left ankle. The knee badge is affixed to the lower seam of the lead apron.

The inner badges will be placed underneath the lead apparel over the left anterior chest.

The cath lab dosimeters will be placed at standard location on the wall at the foot end of the cath lab table.

For the Landauer dosimeters, two badges will be placed at each location (one badge as a backup). 28 badges will be required (14 with and 14 without ControlRad)

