4.6 Catheterization Procedure and EP procedure

Cardiac catheterization, percutaneous coronary intervention, pacemaker and ICD implantation will be performed according to standard guidelines and clinical practice. The ControlRad is only used during fluoroscopy (the device is not used during "cine" acquisition runs). In the event use of the ControlRad device is felt to significantly diminish imaging quality outside the region of interest the device can be turned off. Standard of care views (typically orthogonal) will be performed after PCI to ensure there is no vessel injury.

Each attending physician may perform 1-2 "roll-in" cases to train on the ControlRad system before randomizing patients in the study.

Follow-Up
No clinical follow-up will be performed after the hospital stay since the primary endpoint is radiation dose measured in the cath lab.

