# Table 2. Cumulative Radiation Dose Measured with Aluminum Oxide dosimeter badges (mrem)

# Table 3. Mean Radiation Dose to Physicians and Nurse Measured with RaySafe Dosimeters (mrem)

		ControlRad N=	No ControlRad N=	p-value
Operator 1	Thyroid			
	Knee			
Operator 2	Thyroid			
	Knee			
Anesthesia/Nurs	Thyroid			
е				
	Knee

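### The p-value column in Table 2 (cumulative Landauer badge dose) has no valid basis: each location has one accumulated exposure per arm, so it should be dropped and the table reported descriptively

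*Combined protocol and SAP*

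**What the plan says.** Section 4.4 describes two dosimetry systems.

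- **RaySafe (4.4 A)** is the per-case system: "This dosimeter provides the ability to measure radiation dose" for each case. Its positions in 4.4 C are thyroid and knee for each of three staff roles, plus the wall.
- **Landauer (4.4 B)** accumulates dose over cases at each location: "One set of badges will be used for cases performed with ControlRad, and one set for catheterization cases without ControlRad". Its positions are thyroid and inner (under the lead) for the same three roles, plus the wall.

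For the Landauer badges, 4.4 C adds that "two badges will be placed at each location (one badge as a backup") and that "28 badges will be required (14 with and 14 without ControlRad"). No section describes exchanging badges during the study or reading them at intervals.

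Section 8.0 contains a shell with thyroid, inner and wall rows, one column per arm and a p-value column. The caption that goes with it is "Cumulative Radiation Dose Measured with Aluminum Oxide dosimeter badges (mrem"). Inner positions exist only for the Landauer system, so this shell is Table 2. Section 5.5 specifies intent-to-treat and descriptive summaries, and names no test.

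**The concern.** A p-value for a between-arm difference needs an estimate of how much the result would vary if a different set of procedures had fallen into each arm. The procedure is the unit randomized (4.3). A badge that sums over all procedures in an arm returns one number and discards that variation.

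The practical risk lies in how an empty p-value column gets filled. The only material that looks like replication is the main and backup badge at each location. A two-sample test on those four readings will run and return a number, but its error term reflects how well two badges agree on the same exposure. It says nothing about differences between procedures, so small p-values can appear when the system has no effect on dose.

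**Working it through.** **1. Reproduce the badge count.** Inputs are the position table and the backup rule in 4.4 C.

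- Locations: 3 roles x 2 (thyroid, inner) + 1 wall = 7.
- Badges per arm: 7 x 2 (main and backup) = 14.
- Total: 14 x 2 arms = 28.

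This matches the stated 28, with 14 per arm. The count leaves no spare sets for rotation.

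**2. Degrees of freedom per row of Table 2.** For a two-sample comparison, df = n1 + n2 - 2. With one accumulated exposure per arm, df = 1 + 1 - 2 = 0. A t-test on one value per arm returns no result. The smallest two-sided permutation p-value, 2/C(2k, k) with k independent readings per arm, is 2/C(2,1) = 1.0 at k = 1. This applies to all 7 rows and needs no assumption about variability.

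**3. Backup badge as replicate.** Nominal df becomes 2 + 2 - 2 = 2, but both badges in an arm record the same procedures. If case doses have coefficient of variation (CV) c, the arm total over n cases has CV c/√n. With n = 30 and c = 100%, that is 1/√30 = 18.3%. The main-backup spread contains none of this, only badge error.

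The table gives the simulated type I error at nominal 0.05 with no true difference. Case doses are lognormal, badge errors are independent, and there are 10,000 runs per setting. The documents give neither CV, so both are assumed ranges. The case numbers are 30 per arm (5.3), 80 per arm ((40 + 120)/2, from 1.0) and 160 per arm ((200 + 120)/2, from 3.3).

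| Cases per arm | Between-case CV | Badge CV 2% | Badge CV 5% | Badge CV 10% |
|---|---|---|---|---|
| 30 | 50% | 0.574 | 0.265 | 0.116 |
| 30 | 100% | 0.761 | 0.490 | 0.249 |
| 80 | 50% | 0.396 | 0.150 | 0.076 |
| 80 | 100% | 0.637 | 0.322 | 0.141 |
| 160 | 50% | 0.281 | 0.101 | 0.067 |
| 160 | 100% | 0.519 | 0.214 | 0.108 |

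Every setting exceeds 0.05.

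**4. Other ways to obtain a p-value.** Pooling the 7 locations would give one overall result, not the row p-values in the shell, and the locations share the same cases. Borrowing variance from RaySafe is not specified, and RaySafe has no inner position.

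**5. What can be tested.** RaySafe positions: 3 x 2 + 1 = 7. Those shared with Landauer are 3 thyroid + 1 wall = 4 of 7, where per-case tests are possible. With 30 cases per arm, df = 30 + 30 - 2 = 58. The other 3 of 7 (inner) have no per-case measurement.

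**The case against.** The strongest reply is that this is a heading in an empty template. All the visible shells share the layout, section 5.5 prescribes no test for cumulative dose, and section 3.6 does not list it as an endpoint. No sample size or listed endpoint depends on it. That is correct and limits the reach to minor. It does not make the column usable: the shell still asks for seven p-values that the design cannot supply.

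A reader might infer more from the same passages. The documents do not support these further readings:

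- **That it is unclear whether a badge set follows the randomized arm or actual device use**, because section 4.6 says "the device can be turned off". Section 4.4 C has the badges put on before the procedure starts, while a switch-off for image quality happens during it. No mid-case exchange is described, and 5.5 applies intent-to-treat. The set naturally follows the assigned arm.
- **That EP cases are left out of the Landauer sets**, because 4.4 B mentions catheterization cases for one arm. Section 4.4 uses that word loosely throughout. Read strictly, it would also exclude EP cases from RaySafe. At most this is an optional wording clarification.
- **That the wall-dose secondary endpoint has no usable table cell.** The endpoint in 3.6 is a mean dose in µSv "at a standard location on the wall of the cath lab", whereas Table 2 reports a cumulative dose in mrem, so its wall cell was never the cell for that endpoint. Table 3, titled "Mean Radiation Dose to Physicians and Nurse Measured with RaySafe Dosimeters (mrem"), shows six rows and no wall row. However, the tables in section 8.0 are visibly displaced in the available text, and a final row may have been lost. The title is the only independent hint that it was not planned.

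**Conclusion.** The point holds for Table 2. All 7 p-value cells lack a valid basis, with df = 0 in each row. This follows from the one-set-per-arm rule and the exact 28-badge count, on the reading that badges are neither exchanged nor read at intervals, since no section describes either. It does not depend on the variability assumed in the simulation, which shows only that the backup-badge shortcut is unsafe (type I error 0.067 to 0.761 over the ranges tried).

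The reach is minor. A reader might infer that the main dose comparison is undermined. It is not: the primary endpoint is based on effective dose per case (3.6, 5.2), and RaySafe is the system described as giving per-case dose. The lasting limitation is that the three under-lead locations support no between-arm test, and no listed endpoint calls for one there.

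**What to change.** 1. Delete the p-value column from Table 2. Report cumulative dose, dose per case (cumulative dose divided by the number of cases) and the between-arm ratio as descriptive results, with the number and mix of cases (diagnostic, PCI, EP) in each arm.
2. State that the backup badge is a check on the main reading and not a replicate.
3. State that between-arm tests use the per-case RaySafe data, including wall dose. If the sponsor's Table 3 shell has no wall row, add one and widen the title to match.
4. Note under Table 2 that the inner locations have no per-case measurement and support no between-arm test.
5. Optionally, say in 4.4 B whether EP cases use the same badge sets.

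The cost is one column removed, a few sentences and possibly one table row. No patients, badges or measurements are added, and no valid test is lost.

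A formal test of under-lead dose would need several sets per arm, each worn for different cases and read separately. As a guide, treating the sets as independent and unpaired, 4 per arm would give df = 4 + 4 - 2 = 6 and a smallest permutation p-value of 2/C(8,4) = 2/70 = 0.029, at 4 x 28 = 112 badges. No listed endpoint requires this.

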#### 5.5 Statistical Analysis

Data will be analyzed on an intent-to-treat basis. Continuous variables will be reported as mean  $\pm$  standard deviation, and where appropriate as median  $\pm$  interquartile range. Analyses will be performed by a biostatistician using with SAS software for Windows version 9.3 (or higher).

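### Table 2 compares raw cumulative badge totals between arms, with a p-value, without dividing by the number of cases each badge set recorded

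*Combined protocol and SAP*

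**What the plan says.** Section 4.4 describes two dosimetry methods. RaySafe gives a dose for each case. The other method does not: "The Landauer dosimeter badge will provide a *cumulative* radiation dose for each anatomic location". Section 4.4B assigns the cumulative badges as follows: "One set of badges will be used for cases performed with ControlRad", with a second set for catheterization cases without it. Section 4.4C adds "Prior to each catheterization procedure the radiation badges will be placed at each location" and gives the stock: "28 badges will be required (14 with and 14 without ControlRad", where the second badge at each location is a backup.

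Table 2 is headed "Cumulative Radiation Dose Measured with Aluminum Oxide dosimeter badges (mrem". The shell with thyroid, inner and wall rows belongs to it, since only Landauer badges are worn at the inner site. It has a column for each arm with a blank N, and a p-value column. It has no dose-per-case column, and section 5.5 names neither a test nor a scaling for it.

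Three other places bear on this:

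- Section 4.3 allocates procedures 1:1 by sealed envelope and mentions no blocks or strata.
- Section 4.6 lets each attending physician do one or two "cases to train on the ControlRad system before randomizing patients in the study". It also lets the device be switched off during a case if image quality suffers.
- Section 5.5 states: "Data will be analyzed on an intent-to-treat basis".

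**The concern.** A summed dose is the product of dose per case and number of cases. Comparing sums between arms is fair only if the two badge sets were worn in the same number of cases. The plan neither guarantees equal numbers nor corrects for unequal ones, so Table 2 could show a difference with no device effect, or the wrong size of a true one.

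Two gaps in section 4.4B add to this. Training cases use ControlRad and have no control counterpart. The plan does not say whether study badges are worn in them. Nor does it say that the badge set is chosen by randomised arm, which the intent-to-treat statement would require.

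The p-value is a separate matter. Each location yields one accumulated reading per arm, so there is nothing from which to estimate variation between cases.

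At stake are the supporting cumulative comparison, the under-apron dose (which no other dosimeter measures) and the wall dose. Wall dose is a secondary endpoint in section 3.6, and its only row in the table shells is in Table 2.

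**Working it through.** **1. The plan's badge count.** Three people × 2 sites × 2 badges + 2 wall badges = 14 per set, and 28 for two sets. This reproduces section 4.4C. It confirms one set per arm, shared across all cases, and so one independent total per location per arm. The backup badge is exposed to the same cases and adds no information on variation between them.

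**2. Effect of unequal case numbers alone.** Assume unrestricted 1:1 allocation, equal dose per case and no device effect. The number of cases in one arm has SD √N/2, so a one-SD split gives

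ratio of totals = (N/2 + √N/2) / (N/2 − √N/2)

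- N = 60 (section 5.3, Table 1): 33.87 / 26.13 = 1.30
- N = 120 (EP, section 3.3): 65.48 / 54.52 = 1.20
- N = 200 (catheterization, section 3.3): 107.07 / 92.93 = 1.15
- N = 320 (both, if one pair of sets covers them): 168.94 / 151.06 = 1.12

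The larger total is equally likely to fall in either arm.

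**3. Effect of training cases, if they were badged.** Section 5.3 attributes about 50% of dose to fluoroscopy and cites a 75% reduction of that part, so the whole-case reduction is 0.50 × 0.75 = 37.5%. Take this as true, assume equal dose per case, and put R training cases on the ControlRad set with n randomised cases per arm:

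apparent reduction = 1 − 0.625 × (1 + R/n)

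The plan does not give R. Training cases are optional, so R may be 0. With 35 interventional cardiologists (section 3.3) at two each, the catheterization maximum is 70.

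| n per arm | R = 10 | R = 35 | R = 70 | Break-even R |
|---|---|---|---|---|
| 30 | 16.7% lower | 35.4% higher | 108.3% higher | 18 |
| 100 | 31.2% lower | 15.6% lower | 6.2% higher | 60 |
| 160 | 33.6% lower | 23.8% lower | 10.2% lower | 96 |

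For example, n = 100 and R = 35 gives 1 − 0.625 × 1.35 = 15.6%. The sign turns only when the ControlRad set holds more than 1/0.625 = 1.6 times as many cases as the other set.

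**4. After division by case number.** Under the same equal-dose assumption, total divided by cases worn returns 37.5% whatever the counts, with or without training cases. What remains is chance difference in case mix. By the air kerma medians in section 5.3, a PCI carries 1577/460 = 3.4 times the dose of a diagnostic case.

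**The case against.** A reader might infer that section 4.4B puts every ControlRad case on the badges, training cases included, so that the cumulative comparison will hide or reverse a real reduction. The text does not support that. It is silent on training cases, which section 4.6 makes optional and places before randomisation. The maximum of 70 needs every listed cardiologist to do two. If one pair of sets serves both catheterization and EP (about 160 cases per arm), even 70 would not reverse a 37.5% reduction.

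A reader might also infer that the sets follow device use, against the intent-to-treat statement. Section 4.3 names the arms as with and without ControlRad, so the wording in 4.4B can be read as arm labels. Badges go on before the case and come off at its end, so a case in which the device is switched off would normally stay on its allocated set. No section describes changing sets mid-case.

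Nor is there a fixed bias against the device: chance imbalance in counts runs either way. The count effect can also be undone if the number of cases per set is known, and the blank N in each column could hold that number. The primary endpoint is unaffected, because section 5.2 calculates effective dose per case and RaySafe is the per-case system.

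All of this stands, and it limits the scope of the point. It does not answer three things. The plan does not say that N counts the cases in which a badge set was worn. It describes no division by that count. And it asks for a p-value that a single total per location per arm cannot give.

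**Conclusion.** The point holds for Table 2 as laid out. Raw totals confound dose with case count, and with no device effect a one-SD split moves their ratio to about 1.15 (N = 200), 1.20 (N = 120) or 1.30 (N = 60). These figures assume unrestricted allocation and equal dose per case; blocking, if the envelopes used it, would shrink them. The p-value has no valid basis if, as the badge count implies, each location gives one reading per arm.

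The training-case part is a gap in wording and not a demonstrated error. If such cases were badged they would inflate the ControlRad total: 35 of them at 100 randomised cases per arm would make an assumed 37.5% reduction show as 15.6%. Whether any would be badged, and how many there would be, is unknown.

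The consequences are confined to the results named above under the concern. For the wall dose the harm lies in the tabulation, since section 4.4C also places a RaySafe dosimeter on the wall.

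**What to change.** - In section 4.4B, state that study Landauer badges are worn only in randomised cases, that the set worn is that of the randomised arm whatever the device use during the case, and that study badges are not worn in training cases.
- Record, for each badge set, the number of randomised cases in which it was worn.
- Change Table 2 to cumulative dose divided by that number (mrem per case), with the number shown.
- Remove the Table 2 p-value and present the comparison as descriptive. Inference then rests on the per-case RaySafe data. A wall row in Table 3 would put the wall endpoint on that footing too.

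The cost is two sentences in 4.4B, a case count for each set and a revised table shell, with no added patients, badges or staff. If staff already work this way, the change only documents practice. It is best made before further exposure accumulates: division by case number corrects for counts, but the doses of individual cases cannot be separated once they are on the same badge.
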